### Exploratory:

1. Reactions to mosquito bites by size of wheals/papules, redness of the flare, swelling and itching 30 min post-mosquito feeding (day 43), after two days (day 45) and after 7 days (day 50).
2. Early innate immune response to the mosquito bites in AGS-v PLUS vaccinated participants compared to placebo from biopsies taken from the bite site 2 days post-feeding.
3. *In vitro* viability of Zika virus coated in mosquito saliva after incubation with serum and/or PBMCs from vaccinated participants.
4. Geometric mean concentration and fold increase in Th1 and Th2 cytokine responses (from day 1 to day 43, and from day 43 to day 50) after *in vitro* exposure of PBMCs with mosquito saliva from *Aedes aegypti*, *Aedes albopictus* and *Anopheles gambiae*.

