### 6.1 Screening (Days -60 to 0) (outpatient visit)

- Potential participants will be provided with a verbal description of the study (purpose and study procedures), and will be asked if they have any questions and to read/sign the consent form. The consent form will be signed and potential participants must score  $\geq 70\%$  on a comprehension quiz before the performance of any study procedures. The comprehension quiz may be repeated once.
- The study staff will discuss with the potential participant his/her medical history, study eligibility criteria and concomitant medication use.
- Vital signs (height, weight, oral temperature, blood pressure, heart rate) will be obtained. BMI will be calculated to ensure eligibility.
- Documentation of usual responses to mosquito bites as none (0), mild (1), moderate (2), or severe (3).
- A physical exam will be performed.
- For females who are capable of bearing children, a serum pregnancy test will be performed at the clinical trial study site at the time of screening regardless of age unless written medical demonstration of sterility or amenorrhea (defined as one year with medical evaluation) can be provided.
- A blood sample will be collected from an arm vein to screen for health as follows:
  - Hematology: hemoglobin (Hgb), white blood cell count (WBC), and platelet count;
  - Chemistry: glucose (random), alanine aminotransferase (ALT), and creatinine;
  - Serology: HIV, hepatitis C virus (HCV), and hepatitis B surface antigen (HBsAg).
- Medications taken in the previous 30 days will be recorded.

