#### 6.6 Day 43 Mosquito Feeding (+7 days) (outpatient visit)

The following procedures/assessments and testing will be performed:

- Review of medical/medication history and addition of any new information
- Targeted physician assessment and physical exam if needed
- Vital signs (temperature, heart rate, blood pressure)
- Urine pregnancy test (females of reproductive potential only)
- Blood collection for routine safety labs (hemoglobin, white blood cell count, platelets, serum creatinine, serum alanine aminotransferase, random glucose)
- serum/whole blood for research before mosquito feeding as per [Appendix B](#).
- Mosquito feeding: Starved clean female *Aedes aegypti* and *Aedes albopictus* mosquitoes will be selected from a mosquito colony approved for human feeding studies in Laboratory of Malaria and Vector Research (LMVR), NIAID. Clean mosquitoes are referred to as mosquitoes colonized in an insectary and that are pathogen free. Clean mosquitoes are raised in an incubator dedicated for clinical trials. This ensures these insects are never exposed to human blood after emergence as adult mosquitoes up to the time they are utilized for feeding on human volunteers enrolled in the clinical trial. The insectary has well-established safety precautions to prevent outside mosquitoes from entering the facility. Mosquitoes will be aspirated into a secured Plexiglas feeding device and brought to the CVD from the LMVR Insectary.
  - There will be 10 participants in each treatment arm. Each participant will be exposed to *Aedes aegypti* on the right arm and *Aedes albopictus* mosquitoes on the left arm.

- The feeding site will be wiped clean with mild unscented soap and water and the device will be placed on the participant's arm for 10-20 minutes. The mosquitoes will feed through a disposable mesh on the bottom of the feeding device. This device permits the evaluation of mosquito feeding on the human participant at the end of exposure. In the unlikely event of no feeding or poor feeding (only 0-2 mosquitoes fed or probed as noted by trained staff for a particular strain), the volunteer may undergo a repeat feed with 5-10 fresh mosquitoes ONCE.
  - Participants will be asked not to apply cream, perfume or deodorant on the day of mosquito exposure. Once the mosquitoes have fed they will be brought back to the lab for further study.
  - The PI or study doctor will perform mosquito bite assessments at least 30 min after feeding.
- 
- AE assessment.

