#### **6.7 Day 45 (+/- 1 day) (outpatient visit)**

Two days after the mosquito feeding the participants will return for a follow-up. The following procedures/assessments and testing will be performed:

- Review of medical/medication history and addition of any new information
- Targeted physician assessment and physical exam if needed
- AE assessment
- Mosquito bite assessment
- Collection of 3 skin biopsies: 2 from sites of mosquito bites previously marked by permanent marker, and a third from an unbiten area of normal skin

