### 14.3 Analysis Plan

T-tests will be used to compare immunogenicity endpoint measurements for the primary endpoint and other continuous endpoints between each treatment group and the placebo group. For binary endpoints Fishers exact test will be used. AEs will be tabulated by treatment arm.

The fold increase in cellular and humoral responses to AGS-v PLUS from day 1 to days 43 and 50, and from day 43 to day 50 will be calculated for each participant. The mean fold increases on each active group will be compared to the mean fold increases in the placebo group. The geometric mean antibody titers and geometric mean cytokine concentrations to AGS-v PLUS on days 1, 43, and 50 will be calculated and compared between the different treatment groups.

The fold increase in cellular responses to mosquito saliva from day 1 to days 43 and 50, and from day 43 to day 50 will be calculated for each participant. The mean fold increases on each active group will be compared to the mean fold increases in the placebo group. The geometric mean cytokine concentrations to mosquito saliva on days 1, 43 and 50 will be calculated for each treatment group and compared to placebo.

For the mosquito analysis, the following parameters will be compared on the active groups versus placebo for each mosquito (*Aedes aegypti* and *Aedes albopictus*):

- mean number of days mosquitoes survive after feeding on vaccinated participants
- mean number of eggs laid
- mean number of mosquitoes emerging from the laid eggs

For the visual assessment of the mosquito bite the following parameters will be calculated for each group and active groups will be compared to placebo at three different time points: day 43 (30 min post feeding), day 45 and day 50:

- mean number of visible bites
- mean redness measured across the widest part (mm)
- mean swelling measured using the ball point pen method (mm^2). Ball point pen measurement of induration uses the pen to slide on top of the skin so it halts at the edge of true induration (versus redness)

From the biopsies taken on day 45, the following comparisons will be made:

-gene expression: the level of expression of inflammatory cytokines at the bite site compared to normal skin (control) will be calculated for each participant for each mosquito bite. The mean will be calculated in each group and compared to placebo.

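### Bite redness and swelling are compared with placebo by unadjusted t-test, although a 0-3 bite-response score is collected before randomization and never used; ANCOVA on that score would cost little

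*Combined protocol and SAP*

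**What the plan says.** **Analysis.** Section 14.3 assigns t-tests of each treatment group against placebo to continuous endpoints. For the visual bite assessment it lists the "mean number of visible bites", mean redness at the widest part in mm, and "mean swelling measured using the ball point pen method". These are compared with placebo on Days 43, 45 and 50. No covariate, denominator or count model is given. The mosquito life-cycle measures are explicitly analysed by species; the visual measures are not.

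**Endpoint.** The first exploratory endpoint in section 3.2 is "Reactions to mosquito bites by size of wheals/papules, redness of the flare, swelling and itching 30 min post-mosquito feeding" and at the two later visits. Neither this definition nor section 7.3 (Mosquito Bite Assessment) mentions a count of bites.

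**Baseline.** The screening visit (section 6.1) includes "Documentation of usual responses to mosquito bites as none (0), mild (1), moderate (2), or severe (3"). Appendix A places randomization on Day 1, so the score precedes it.

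**Exposure.** Section 6.6 lets feeding last 10-20 minutes. If "only 0-2 mosquitoes fed or probed as noted by trained staff for a particular strain", then "the volunteer may undergo a repeat feed with 5-10 fresh mosquitoes ONCE". How bites from a repeat feed enter the count is not stated.

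**Biopsy.** Section 6.7 takes three skin biopsies on Day 45, "2 from sites of mosquito bites previously marked by permanent marker". Section 8.6 (Risk of Skin Biopsies) makes these one bite per species. Section 6.8 then lists bite assessment and biopsy healing as separate Day 50 items.

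**The concern.** How strongly a person reacts to mosquito bites varies between people, and the plan already asks about it before randomization. With 10 per arm, leaving out a baseline measure aimed at the same trait may give up precision in redness and swelling, the two analysed measures closest to the defined endpoint.

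The bite count has a separate difficulty of interpretation. It reflects how many mosquitoes fed or probed as well as how the skin responded, and exposure can differ between participants. If the vaccine changes feeding, a difference in raw counts need not mean a difference in skin reactivity. On Day 50, one bite per species has already been biopsied, and section 14.3 does not say whether that site is still counted or measured.

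**Working it through.** **1. Inputs.** Ten participants per arm (sections 3.1 and 6.6). One-sided alpha 0.1 and 0.95 SD come from section 14.2, where they belong to the primary immunogenicity endpoint. They are borrowed here as assumptions, because no effect size, SD, alpha or direction is stated for bite reactions. The share of variance explained by the score (R-squared) is not in the documents; 0 to 0.3 is shown.

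**2. The plan's own t-test figure.** Noncentrality = 0.95 / sqrt(1/10 + 1/10) = 0.95 x sqrt(5) = 2.124. With 18 df the one-sided 0.1 critical value is 1.330 and power is 0.786 (normal approximation 0.800). Section 14.2 states at least 85%, which these inputs do not reproduce. That is a separate matter; here it only fixes the unadjusted starting point. Simulation gives about 0.78.

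**3. Adding the screening score as one linear covariate.** Residual SD is multiplied by sqrt(1 - R-squared), df fall to 17 (critical value 1.333), and chance imbalance in the covariate inflates the variance by about 1 + 1/16 = 17/16. So noncentrality = 2.124 x sqrt(16/17) / sqrt(1 - R-squared).

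| R-squared | Noncentrality | Power, formula | Power, simulation |
|---|---|---|---|
| 0 | 2.06 | 0.77 | 0.77 |
| 0.1 | 2.17 | 0.80 | 0.79 |
| 0.2 | 2.30 | 0.83 | 0.84 |
| 0.3 | 2.46 | 0.87 | 0.87 |

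The two columns agree to about 0.01. Break-even is near (16/17) / (1 - R-squared) = 1, that is R-squared of about 1/17 = 0.06.

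**4. Raw count against bites per mosquito.** Simulated with 10 per arm and one-sided 0.1, assuming 5 or 10 mosquitoes in the first exposure, mean feeding probability 0.5-0.9 varying between hosts, and a repeat of 5-10 after 0-2 fed.

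- No vaccine effect: the raw count rejects in 0.097-0.105 of trials and bites per fed mosquito in 0.095-0.101. Chance variation in feeding does not bias the raw test.
- Visible bites per fed mosquito fall from 0.8 to 0.6: power is 0.43-0.73 raw and 0.62-0.82 per fed mosquito.
- Vaccine lowers feeding probability by 0.2 and nothing else: raw rejects in 0.23-0.62 of trials, the ratio in about 0.09-0.10. The two analyses answer different questions.
- Variant with 10 exposed and no repeat feed, where 30-60% of unfed mosquitoes probe and leave bites and the vaccine lowers feeding: bites per fed mosquito rise from 0.97 to 1.22, or from 1.15 to 1.64. The test then wrongly favours more bites with vaccine in 0.41-0.52 of trials. Dividing by fed plus probed gives about 0.10.

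**5. Day 50.** One bite per species is biopsied in every participant. If 3-10 bites per species were made (an assumption), that is 1/10 to 1/3 of them, alike in all arms.

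**The case against.** **The score may be weak.** It is a coarse, recalled 0-3 item, and nothing in the documents shows that it predicts measured redness or swelling. If it does not, adjustment loses about 0.01 of power. This stands, and it is why the gain is given as a range.

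**The endpoint is exploratory, with 10 per arm.** This also stands and limits the priority. Within the endpoint, the bite count is secondary: it appears in neither the endpoint definition nor section 7.3.

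**A reader might infer that dividing by the number fed is simply better.** The documents do not support that. The number fed arises after randomization. Section 1 describes the transmission-blocking aim as preventing blood feeding itself, so the vaccine may change that number. Probing can leave bites too, and zero fed leaves the ratio undefined. The raw count keeps its error rate when feeding does not differ by arm.

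**A reader might infer that all inputs are already recorded.** Section 6.6 has staff note poor feeding and says the device allows feeding to be evaluated; section 7.1.1 removes fed mosquitoes for follow-up. A fed count is therefore obtainable. No text names the numbers fed, probed or repeat-fed as data items.

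**A reader might infer that repeat feeds create a false increase.** Assume 3-10 fed per site, 90% of bites visible, and repeats in 30% of active participants only. The raw count then shows a false increase in 0.22 of trials, but only if every repeat mosquito feeds. At 80%, 65% or 50% feeding it is 0.13, 0.07 or 0.04. The means explain this: a repeat-fed site has 1 + 7.5 = 8.5 fed if all feed, but 1 + 0.65 x 7.5 = 5.9 at 65%, against 6.5 for an ordinary site. The repeat rule does not inherently inflate counts.

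**Biopsy affects all arms alike**, and the plan nowhere says that wounds are counted as bites. The Day 50 point is a clarification, not a demonstrated bias.

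**Conclusion.** The point holds as a low-cost improvement. A baseline score taken before randomization is left out of the redness and swelling comparisons. Under the borrowed 0.95 SD effect, 10 per arm and one-sided 0.1, ANCOVA takes power from about 0.78 to about 0.79, 0.84 or 0.87 at R-squared 0.1, 0.2 or 0.3, and to about 0.77 at R-squared 0. The benefit is negligible at 0.1 and worthwhile from about 0.2. Which applies cannot be determined from the documents.

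The raw count is a valid randomized comparison whose meaning is mixed. It should be kept and supplemented, not replaced. No primary or secondary conclusion of the trial depends on any of this.

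**What to change.** In section 14.3:

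1. Compare redness and swelling with placebo by ANCOVA, with the 0-3 screening score as a single linear covariate. Cost: analysis wording and 1 df.
2. Keep the raw visible-bite count as the randomized comparison. Record, for each participant and species, the numbers of mosquitoes that fed or probed, including any repeat feed, and report them by arm as a result in their own right.
3. As a supportive analysis, give visible bites per mosquito fed or probed, by species, with repeat feeds in the denominator. A count model with the log of that number as offset would serve. State how a participant with none fed or probed is handled, and that the denominator is post-randomization.
4. State that Day 50 bite count, redness and swelling use unbiopsied bites only, in every arm.

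Items 2 and 3 need explicit data fields for the counts, and item 4 needs the biopsied site to be identifiable in the bite record. No participant procedure is added. All of it should be fixed before the Day 50 unblinding.

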## 6.2 Enrollment/Baseline and First Vaccination (Day 1) (outpatient visit)

Randomization will use computer generated randomization codes. These codes will be sent to the pharmacy where the unblinded pharmacist will have the key and prepare the appropriate agent for administration. All vaccination syringes will be labeled to cover contents so that the blinded staff cannot identify the different treatments.

The first vaccine or placebo administration will take place on Day 1. The research team will confirm continuing consent with the volunteer before performing any and all procedures. Once it is determined that the participant still meets inclusion/exclusion criteria for the research study, participants will receive the first of two injections.

The following procedures will be performed at enrollment:

- Review of medical/concomitant medication history
- Targeted physical exam/assessment as needed
- Vital signs pre-vaccination
- Vital signs 30-45 minutes post vaccination
- Blood collection for routine safety labs (Hemoglobin, white blood cell count, platelets, serum creatinine, serum alanine aminotransferase, random glucose)
- serum/whole blood prevaccination for research (as per [Appendix B](#))
- Urine pregnancy test (females of childbearing potential only)
- Review of inclusion/exclusion criteria
- Vaccine or placebo administration
- Vaccine injection site and AE assessment pre-vaccination and 30-45 minutes post vaccination
- AE memory aid, thermometer, and ruler will be distributed before discharge home

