#### 7.1.1 Laboratory Testing of Collected Samples for Primary and Secondary Endpoints

- AGS-v PLUS specific IgG, IgM and IgE assay will be performed using enzyme-linked immunosorbent assay (ELISA). The time points assayed will be day 1, day 43 and day 50.
- Th1 and Th2 response assays: PBMCs collected from participants will be incubated with AGS-v PLUS and saliva from *Aedes aegypti*, *Aedes albopictus* and *Anopheles gambiae* and measurements of Th1 (Interferon-gamma) and Th2 (Interleukin-4) cytokines will be performed using ELISA. The time points assayed will be day 1, day 43 and day 50.
- Biopsies taken on day 45 will be used to assess expression of inflammatory markers.
- Feeding on human volunteers: 24 hour after emergence from pupae, male and female *Aedes aegypti* and *Aedes albopictus* mosquitoes will be allowed to mate for 24-48 hours. After this period, female mosquitoes will be separated from males. These mosquitoes would have only been sugar-fed up until now. Female mosquitoes will be placed in a secured Plexiglass feeding device and allowed to feed on the volunteer's arms on Day 43 (approximately 21 days after they have completed the vaccination schedule). Each participant from each arm will be exposed to the bites of *Aedes aegypti* on the right arm and *Aedes albopictus* on the left arm. Mosquitoes that had a blood meal will then be removed and followed up to assess any changes to their life cycle, i.e., life-span, number of eggs laid, number of fertile eggs, number of surviving larvae etc. The mosquito colony used in this study will not be fed on human blood before exposure to participants, but on non-mammalian blood to minimize the presence of blood borne pathogens.
- Zika virus killing, *in vitro* toxicity assay:
  - Blood samples will be obtained from all volunteers 21 days after vaccination is completed (day 43 pre-feeding). PBMCs+sera containing immune cells and antibodies generated against AGS-v PLUS will be tested for their ability to kill or inactivate Zika virus coated with salivary gland proteins from *Aedes aegypti* and *Aedes albopictus*. Viability of the virus will be tested by infecting Vero cells with the PBMC/virus supernatants. Infectivity of the Zika virus will be assessed by measuring the viability of the Vero cells using MTT assay.
  - Zika virus will be obtained from commercial suppliers and will be propagated *in vitro*.

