The viability/infectivity of Zika virus after culture with PBMCs and serum from vaccinated participants will be assessed by infecting Vero cells with the cell supernatant followed by measuring viability of Vero cells using MTT assay. The higher the infectivity of the Zika virus the lower the MTT value will be for Vero cells. The fold changes from day 0 to day 43 will be measured for each participant and the mean calculated for each group and compared to placebo.

For randomization, the first 10 participants will be randomized into 5 arms with 2 in each arm. An interim safety analysis after the first group of 10 participants have received the first immunization and completed the Day 8 phone call will be done by the DSMB by teleconference. Recruitment activities will continue but vaccination of new participants will be halted until the DSMB review has been completed. Once the interim safety analysis is done on the initial enrolment, an additional set of 40 participants will be enrolled and randomized using a permuted block randomization with a block size of 10.

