**Appendix A: Schedule of Procedures/Evaluations**

Study Phase >	Screen	Injec tion 1	Follow -up call	Injec tion 2	Follow -up call	Feedin g	Follow -up	Follow- up	Follow -up	Follow -up call
Study Day >	DAYS -60 to 0	D1	D8	D22	D29	D43	D45	D50	D181	D366
Outpatient Visit	X	X		X		X	X	X		
Comprehension quiz	X									
Written Consent	X									
Medical/Medication History	X	X	X	X	X	X	X	X	X	X
Physician Assessment and PE (targeted and as needed after screening)	X	X		X		X	X	X		
Review of inclusion/exclusion criteria and review of consent	X	X		X						
Vital signs (temperature, heart rate, blood pressure)	X	X		X		X		X		
Vital signs, Vaccine injection site and AE assessment pre-vaccination and 30-45 min post-vaccination		X		X						
Provision of memory aid, ruler and thermometer		X		X						
Review of AEs			X	X	X	X	X	X		
Review of Memory Aid			X		X					
Telephone Call to Assess Symptoms and AEs			X		X				X	X
Pregnancy test (serum/urine) ‡	X	X		X		X				
Vaccine administration		X		X						
Randomization		X								
Mosquito Feeding						X				
Mosquito Bite Assessment						X	X	X		
Safety Labs: hemoglobin, white blood cells, platelets, serum creatinine, serum alanine aminotransferase, random glucose	X	X		X		X		X		
Screening Labs: HIV, hepatitis B and C	X									
Serum and Whole Blood Collection		X				X		X		
Skin Biopsy							X			
Skin Biopsy inspection								X		

† Vital Signs: participants must be sitting for a minimum of 5 minutes before these procedures being performed; vital signs include blood pressure, heart rate, temperature. Weight and height will be taken at the screening visit only.

‡ Serum pregnancy testing at the screening and urine pregnancy testing for all other visits. On Days 1, 22, 43, study vaccination or mosquito feeding will not be initiated until negative results are available. Females of childbearing potential only.

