**Appendix B: Blood Volumes for Specimen Collection**

Study Schedule/Procedures	Volume	Screening	Day 1 prevaccination	Day 22 prevaccination	Day 43 (pre-mosquito feeding)	Follow-up Day 50
Serum creatinine, serum alanine aminotransferase, hepatitis BsAg, hepatitis C Ab & b-hCG, Pregnancy, if needed	8.5 mL per blood draw	8.5 mL	x	x	x	x
HIV	3.5 mL	3.5 mL	X	X	X	X
Complete blood count	4 mL per blood draw	4 mL	4 mL	4 mL	4 mL	4 mL
Serum creatinine, serum alanine aminotransferase	5 mL per blood draw	x	5 mL	5 mL	5 mL	5 mL
Serum for Immunology studies	4mL	x	4mL	x	4ml	4mL
Whole blood for Immunology studies	50 mL	x	50 mL	x	50 ml	50 mL
Daily Volume (mL)		16 mL	63 mL	9 mL	63 mL	63 mL
Cumulative Volume			79 mL	88 mL	151 mL	214 mL

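### The Zika fold change in 14.3 starts from a Day 0 that has no research sample, and 7.1.1 names only Day 43 blood for the assay; the Day 1 run that would supply the baseline is not specified

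*Combined protocol and SAP*

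**What the plan says.** Section 14.3 describes the Zika analysis as a within-participant ratio, averaged by group and set against placebo: "The fold changes from day 0 to day 43 will be measured for each participant".

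Section 7.1.1 describes the laboratory work. On sampling it says: "Blood samples will be obtained from all volunteers 21 days after vaccination is completed (day 43 pre-feeding". On the material it says: "PBMCs+sera containing immune cells and antibodies generated against AGS-v PLUS will be tested for their ability to kill or inactivate Zika virus". It names no earlier sample for this assay. The antibody and cytokine bullets in the same section each list Day 1, Day 43 and Day 50.

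Research blood before the first dose is scheduled. Section 6.2 lists, for Day 1, "serum/whole blood prevaccination for research (as per" Appendix B). Appendix A marks the row "Serum and Whole Blood Collection" at Days 1, 43 and 50. Appendix B gives volumes for "Serum for Immunology studies" and "Whole blood for Immunology studies" at those same three visits.

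Day 0 appears in two other senses. Section 3.1 places the doses at Days 0 and 21 and then lists the same doses as day 1 and day 22. Section 6.1 makes Day 0 the last day of the screening window.

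**The concern.** A fold change needs two assay results per participant. A laboratory working from 7.1.1 would run Day 43 only, and a statistician working from 14.3 would then have no denominator. Elsewhere in 14.3 the antibody and cytokine fold increases start from day 1; only the Zika paragraph starts from Day 0. The endpoint definition does not settle it: exploratory endpoint 3 gives no time point, whereas exploratory endpoint 4 does.

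The timing matters because pre-vaccination material cannot be redrawn after the first dose. The PBMCs (peripheral blood mononuclear cells) from Day 1 must also supply cultures with the vaccine antigens and with saliva from three mosquito species, and the documents do not say how the cells are shared out. If nobody has been told to keep Day 1 cells for the Zika assay, they may be used up. This is the protocol's only functional antiviral readout.

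**Working it through.** **1. Is there a baseline sample?** Adding up Appendix B:

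- Screening: 8.5 + 3.5 + 4 = 16 mL (stated 16), none of it research blood.
- Day 1: 4 + 5 + 4 + 50 = 63 mL (stated 63), of which research blood is 4 + 50 = 54 mL.
- Day 22: 4 + 5 = 9 mL (stated 9).
- Day 43: 4 + 5 + 4 + 50 = 63 mL (stated 63), again 54 mL for research. Day 50 is the same.
- Cumulative: 16 + 63 = 79; + 9 = 88; + 63 = 151; + 63 = 214 mL, as stated.

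The table is read correctly, and matched pre- and post-vaccination samples of serum and whole blood exist. No research blood falls in screening, so Day 0 in the sense of section 6.1 cannot supply the baseline.

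**2. What does Day 0 mean in 14.3?** Under section 6.1 it is the end of screening, with no usable sample. Under section 3.1 it is the first dosing day, which the visit schedule calls Day 1 and on which a pre-vaccination sample is taken. The second reading is much the more plausible.

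**3. Does 7.1.1 call for that sample to be assayed?** No. The antibody and cytokine bullets name Day 1; the Zika bullet does not.

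**4. If Day 1 is assayed, how should it be used?** Section 14.3 does not put the Zika fold change on a log scale. On the log scale, take equal variances on the two days and a correlation r between them. The variance of a between-arm difference, relative to using Day 43 alone, is:

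- log fold change: 2(1 − r)
- Day 43 alone: 1
- Day 43 adjusted for Day 1, large samples: 1 − r²

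With 10 per arm (section 3.1), estimating the slope multiplies the last factor by about 1 + 1/(18 − 2) = 17/16. This assumes a normally distributed baseline and an analysis of each active arm against placebo, which has 18 within-arm degrees of freedom for the baseline. Residual degrees of freedom fall from 18 to 17.

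| r | log fold change | Day 43 alone | adjusted, large sample | adjusted, 10 per arm |
|---|---|---|---|---|
| 0.3 | 1.40 | 1 | 0.91 | 0.97 |
| 0.5 | 1.00 | 1 | 0.75 | 0.80 |
| 0.7 | 0.60 | 1 | 0.51 | 0.54 |
| 0.9 | 0.20 | 1 | 0.19 | 0.20 |

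The fold change is less precise than Day 43 alone when r is below 0.5. At 10 per arm the adjusted comparison beats Day 43 alone once r² exceeds 1/17 (r above about 0.24). It beats the fold change until (1 + r) × 17/16 reaches 2, that is r = 15/17, about 0.88; beyond that the two are nearly equal. The documents give no value for r, so the table is a range and not an estimate.

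**The case against.** The strongest reply is that this is a small wording gap. Day 1 blood is drawn from everyone, section 3.1 shows that Day 0 is a second name for the first dosing day, and a plan to measure a fold change itself implies a baseline run. Section 7.1.1 is headed for primary and secondary endpoints, so its Zika bullet may not be meant as a full list of time points; it does not say that Day 43 is the only one. Exploratory endpoint 3 specifies no fold change, so a randomised comparison at Day 43 would still answer it.

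Most of this stands, and it rules out the stronger reading that a reader might infer: that no baseline sample exists and the statistic cannot be computed. The sample does exist. Nor do the documents show that no participant will have a baseline result; that follows only if silence in 7.1.1 is taken as exclusion. A reader might also expect batch drift between Day 1 and Day 43 runs, but plate layout, batching and assay timing are not described, so drift is a possibility to guard against and not a finding.

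What the reply does not remove is that the laboratory instruction and the analysis disagree on their face, and that the sample needed cannot be replaced. The preference for an adjusted analysis is a separate gain in precision and is not needed to show the inconsistency.

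**Conclusion.** The point holds as an inconsistency between sections 7.1.1 and 14.3, not as an endpoint that cannot be analysed. The fold change is recoverable if, and only if, the Day 1 pre-vaccination sample is put through the Zika assay. The reach is one exploratory endpoint; primary and secondary endpoints, sample size and safety rules are untouched. It is a minor point, worth settling before the Day 1 cells are allocated.

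The conclusion assumes that Day 0 in 14.3 means the first dosing day, and that enough Day 1 PBMCs and serum remain after the other assays. The documents support the first through section 3.1 and are silent on the second. The precision comparison also rests on equal log-scale variances and an unknown correlation.

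**What to change.** - In 7.1.1, state that the Zika assay is run on both Day 1 pre-vaccination and Day 43 pre-feeding samples, preferably in the same run for each participant. Confirm that enough Day 1 PBMCs and serum are set aside for it.
- In 14.3, change Day 0 to Day 1. Replace the comparison of mean raw fold changes with a comparison of log Day 43 values, each active arm against placebo, adjusted for log Day 1.
- If Day 1 will not be assayed, drop the fold change and compare the arms directly at Day 43.

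The first route costs extra assay wells and one degree of freedom for the covariate. The number of wells cannot be worked out from the documents: 7.1.1 uses salivary proteins from two *Aedes* species, and replicates are not stated. No extra blood draw is scheduled by this change. The Day 43 route needs only a wording change and gives up any precision that the baseline would add.
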